# **Study Summary**

Title	COVID-FIS: A Phase 2 Placebo-Controlled Pilot Study in COVID-19 of Fisetin to Alleviate Dysfunction and Excessive Inflammatory Response in Older Adults in Nursing Homes	
Running Title	COVID-FIS: COVID-19 Pilot Study of Fisetin to Alleviate Dysfunction and Inflammation	
Protocol Number	20-008867	
Phase	Phase II	
Methodology	Randomized, placebo-controlled, double-blind secondary prevention trial	
Overall Study Duration	32 months	
Subject Participation Duration	Subject participation duration 6 months (screening, 4 days treatment, follow-up visits, unblinded at the end of the study)	
Single or Multi-Site	Multi-Site	
Objectives	
 
To prevent COVID-19 (CoV) disease complications by a 7 point score adapted from the WHO Ordinal Scale for Clinical Improvement of CoV (Appendix 1)
 
To evaluate safety and tolerability of Fisetin in this patient population
 
To reduce progression of severity of SARS-CoV-2 infections with no, mild, or moderate to severe or critical symptoms. To decrease senescent cells, inflammation, and physical dysfunction (frailty)
 
	
Number of Subjects	250 enrolled and screened, 150 accrued and randomized	
Diagnosis and Main Inclusion Criteria	Women or men age $\geq$ 65 years in a nursing home with mRNA-PCR test-proven CoV infection. SpO2 $\geq$ 85% (on room air or $\leq$ 2 L of supplemental oxygen) at time of enrollment.	
Study Product, Dose, Route, Regimen	This study will involve a 2-day oral or NG or D tube course of Fisetin twice (~20 mg/kg/day for 2 consecutive days; Days 0, 1, 8 and 9).	
Duration of Administration	4 out of 10 days	
Reference therapy	Reference therapy Placebo-controlled	
Statistical Methodology	Assuming 75 subjects/ group with a significance level of 0.05, the study will have 80% power to detect an odds ratio of 2.24 comparing the placebo- to Fisetin-treated group, using the 7-point severity score at Day 14 as the endpoint in an ordinal logistic regression model.	

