## 2 Study Objectives

#### 2.1 Primary Objectives

The primary objective is to test the efficacy of the senolytic drug (Fisetin) in preventing or delaying progression of CoV severity in nursing home patients with proven CoV according to a 7 point scale for nursing home CoV severity adapted from the WHO Ordinal Scale for Clinical Improvement of CoV\*:

- Not hospitalized nor on additional oxygen (compared to baseline), at baseline level of function (as assessed by activities of daily living).
- Not hospitalized nor on additional oxygen, but below previous level of function.
- Hospitalized or moved to a more intensive unit within the nursing home because of additional dysfunction (not simply because of positivity), but not requiring additional oxygen nor placed on an antiviral drug for worsening CoV symptoms.
- Hospitalized or moved to a more intensive unit within the nursing home and requiring additional oxygen (vs. baseline) and/ or placed on an antiviral drug for worseningCoV symptoms.

- Hospitalized or moved to a more intensive unit within the nursing home and requiring additional oxygen by ECMO or ventilator.
- Transferred to palliative care to provide end-of-life care.
- Death.

\*The WHO Ordinal Scale for Clinical Improvement of CoV (Appendix 1) is scored from 0 to 8 with 0 = no evidence of infection to 8 = death. Our adapted scale does not include scores 0 or 1, since no subjects in COVID-FIS will meet these criteria (e.g., all subjects have proven CoV infection, so none have "no infection").

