# 6.2 Baseline (Day 0 & Day 1) – IP Administration

The following evaluations are to be completed at the screening or Day 0 visit. The investigator must have confirmed eligibility before proceeding with randomization on the Day 0 visit. Participants should complete the following assessments before being administered IP if feasible.

Patients who meet eligibility criteria, including a positive SARS-CoV-2 PCR and, during the influenza season, a rapid influenza and RSV test at a Mayo Clinic or other CLIA certified laboratory before randomization, and do not have evidence of unstable (as *per* clinical judgment) anemia, diabetes, liver disease, or renal dysfunction:

- Eligibility confirmation.
- Determination of Ordinal Scale score.
- Review of concomitant medications.
- Review of adverse events.
- Vital signs heart rate, temperature, blood pressure, body weight, oxygenation (use of supplemental oxygen, amount of supplement oxygen used and Sp02 (if possible)) and respiratory rate. Collection of most recent (at least within 100 or fewer days) Minimal Data Set (MDS) on record for that participant).
- If clinical chest imaging (X-ray, CT, MRI) is performed during the subject's participation in the study or within 14 days prior to enrollment, results may be obtained.
- The 1st IP administration will occur on Day 0. The 2nd IP administration will occur on Day 1 (12 to 36 hours after the 1st IP administration).

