# 8 Statistical Plan

### 8.1 Sample Size Determination

Power calculations for the comparison of the Fisetin and control groups were made assuming an equal distribution among the 7-point scale categories at Day 14 among the controls using a two-sided significance level of 0.05 (alpha). With 75 subjects per group, the study would have 80% power to detect a log odd's ratio of 0.81 which translates to an odd's ratio of 2.25 comparing the control to Fisetin group. Power calculations were run using the PASS software package.

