#### 8.2 Statistical Methods

All participants who are randomized will be included in the primary efficacy analysis. The analysis will follow the ITT principle (*i.e.* according to the treatment arm they are randomized to). For the primary analysis using the values of the 7-point scale, we will test the coefficient of the treatment effect (as a fixed effect) in an ordinal logistic regression model using a 2-sided 0.05 level Wald test after adjusting for key baseline variables such as baseline COVID severity status, age, and sex that show imbalance between the groups. Subjects who withdraw early but received at least some treatment will have their last known values carried forward until they complete the study at Day 180±14. All participants who receive any dose of drug (Fisetin or placebo) will be included in the safety and tolerability evaluation. The definitions of adverse events are described in Sections 9.1-9.3. Participants will be assessed over the entire period of drug administration. Frequency tables will be generated to summarize the occurrence of AE's by treatment arm. Comparisons of the rates of individual AEs will be done using tests of proportions such as the Fisher's exact test or Chi-squared test.

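### Baseline COVID severity status in the primary model is undefined, and the ordinal score scheduled at Day 0 would be a compressed stand-in, largely blind to oxygen need at entry

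*Combined protocol and SAP*

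**What the plan says.** Section 8.2 fits an ordinal logistic model to the 7-point scale and tests treatment with a two-sided 0.05 Wald test "after adjusting for key baseline variables such as baseline COVID severity status, age, and sex that show imbalance between the groups". It does not say how baseline severity is measured.

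Sections 6.1 and 6.2 and Appendix 2 schedule an ordinal score at screening and Day 0. No other severity score is listed there. The 2.1 scale opens with "Not hospitalized nor on additional oxygen (compared to baseline), at baseline level of function (as assessed by activities of daily living". Level 2 has the same oxygen condition, with function below its previous level. Levels 3 to 5 all require hospitalisation or a move to a more intensive unit. Level 4 adds extra oxygen compared with baseline, an antiviral for worsening symptoms, or both. Section 2.1 does not say whether baseline is study entry or the state before infection. Section 7.3 names the Appendix 1 scale, the WHO 0 to 8 scale, as the one recorded.

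Inclusion criterion 3 admits residents with moderate or lesser severity, or with SpO2 of at least 85% on room air or up to 2 L of oxygen. The vital signs in 6.2 include "oxygenation (use of supplemental oxygen, amount of supplement oxygen used and Sp02 (if possible)) and respiratory rate", and 6.1 has the same item. Section 5.3 randomises without stratification. Section 3.1 mentions stratifying on antiviral use should that become standard of care, but no section stratifies on severity.

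**The concern.** Oxygen need and saturation at entry plausibly predict the Day 14 score. The ordinal score is the natural candidate for the undefined covariate, since it is the one severity score on the schedule, but it is built to record change from baseline rather than to rank residents at baseline.

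Under the 8.2 rule the choice matters twice. A variable that barely separates entrants adjusts for little. Because adjustment is triggered by imbalance, it may also fail to show the imbalance that would trigger it. With the term left open, the analyst could choose the measure after seeing the data, in the trial's primary test.

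**Working it through.** **1. The plan's own figure.** Section 8.1: 75 per group, log odds ratio 0.81 (OR 2.25; the Study Summary says 2.24), two-sided alpha 0.05, and "assuming an equal distribution among the 7-point scale categories at Day 14 among the controls". Whitehead's formula is n per arm = 6(z₁₋α/₂ + z₁₋β)² / [(log OR)²(1 − Σp̄³)], where p̄ is the mean of the two arms' category probabilities. With control probabilities of 1/7 and OR 2.25, Σp̄³ = 0.024, so

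n = 6 × (1.960 + 0.842)² / (0.811² × 0.976) = 73.4.

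Power at 75 per arm is 80.9% for OR 2.25, 80.8% for log OR 0.81 and 80.4% for OR 2.24. The stated 80% is reproduced. The calculation has no covariate.

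**2. Scoring two eligible residents at Day 0.** These are illustrative records, not data. A has no symptoms and SpO2 97% on room air. B has moderate symptoms and SpO2 86% on 2 L, and is cared for in place.

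| Scale and reading | A | B |
|---|---|---|
| 2.1, baseline = study entry | 1 | 1, or 2 if function is compared with an earlier state |
| 2.1, baseline = before infection, oxygen long-standing | 1 | 1 or 2 |
| 2.1, baseline = before infection, oxygen new | 1 | No level fits: 1 and 2 exclude additional oxygen; 3 to 5 need hospitalisation or a unit move |
| Appendix 1 | 2 (the note in 2.1 says nobody will score 0 or 1) | 2 (the oxygen scores sit under the hospitalised states) |

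On no reading does the score cleanly separate the two by oxygen need. Levels 3 and 4 are reached only after hospitalisation or a unit move; level 4 then needs new oxygen or an antiviral.

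**3. Chance of imbalance in a marker the score misses.** Let a share p of entrants be on oxygen (assumed; the documents give no figure). The arm difference has SD √(2p(1 − p)/75). For p = 0.30 this is √(0.42/75) = 0.075, and the two-sided chance of a difference of at least 10 points is 2[1 − Φ(0.10/0.075)] = 18%. For p = 0.10 and p = 0.50 it is 4% and 22%.

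**4. Value of a severity covariate.** Simulations used 75 per arm, a uniform control outcome, a conditional OR of 2.25 and an assumed normal severity variable. Monte Carlo error is about 2.5 points with 300 runs and 4 points with 120.

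| Set | Severity effect (log odds per SD) | Power, no covariate | Power, with covariate |
|---|---|---|---|
| 300 runs | 0.5, 0.8, 1.1 | 78%, 71%, 65% | Exact severity: 81%, 81%, 76% |
| 120 runs | 0.5, 1.0, 1.5 | 73%, 67%, 60% | Two levels tracking severity: 74%, 78%, 75%; four levels: 76%, 77%, 82% |
| 120 runs | three increasing strengths | 78%, 69%, 62% | Exact severity: 79%, 76%, 82%; binary oxygen-type marker: 80%, 71%, 73% |

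The no-covariate column is not a shortfall from the planned 80%. With the conditional OR held at 2.25, omitting severity shrinks the marginal log OR to about 0.78, 0.73 and 0.68 in the 300-run set. Since √(75 × 0.976/6) = 3.493, power is Φ(3.493 × 0.78 − 1.96) = 78%, and likewise 72% and 66%. That accounts for 78%, 71% and 65%. Section 8.1 applies OR 2.25 without a covariate, so its 80% stands on its own terms.

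**The case against.** The strongest reply is that 8.2 never names the Day 0 ordinal score. Elsewhere the protocol uses severity for a symptom grading: criterion 3 refers to moderate or lesser severity, and 3.5 to no, mild or moderate symptoms, citing a Table 4 that is not in the text I have and that I do not judge. This reading is fair, so the point must be conditional. It does not settle the matter. The visit sections list overall symptoms, if feasible, and eligibility confirmation, but no symptom grade as a recorded item.

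A reader might infer that the score cannot serve as a covariate at all, or that adjusting for it does nothing. The documents do not support that. Levels 1 and 2 differ in function, levels 3 and 4 can be reached inside the nursing home, and in simulation a two-level covariate that tracks severity recovers much of the power. A reader might also infer that an oxygen imbalance would go undetected. It need not: oxygen use is recorded at screening and Day 0, and the covariate list in 8.2 is open, so such an imbalance could be seen and adjusted for under the present wording. Nothing obliges anyone to do so.

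Two further points stand. No simulation tests the Day 0 score itself. And absolute oxygen use mixes long-standing need with need caused by COVID, which the baseline-relative wording tries to separate. That is a reason to allow the Day 0 score alongside oxygen use, not to rely on it alone.

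**Conclusion.** The point holds as a conditional one. Baseline COVID severity status is undefined in the primary model and enters only on observed imbalance. If the scheduled Day 0 ordinal score fills the gap, it will be compressed on either scale and largely blind to oxygen need at entry, making it a weak covariate and a weak imbalance check. That most entrants score 1 or 2 is inferred from the scale and the entry criteria, not from data.

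The size depends on how strongly entry severity predicts the Day 14 score, which is assumed. The gain runs from negligible (78% to 79%) to roughly 10 points or more (71% to 81%; 62% to 82%). It is smaller for a binary oxygen-type marker: about 2 points at the two lower strengths (78% to 80%, 69% to 71%) and 11 at the highest (62% to 73%). The design's 80% power is correct as stated and should not be read as being in doubt. This should be changed, but it does not undermine the design.

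**What to change.** In 8.2, define baseline severity as supplemental oxygen use (none versus any, up to 2 L under the oxygen limb of criterion 3) plus SpO2 as a continuous variable where available, each taken as the last value before the first dose. Include both in the primary ordinal model regardless of observed imbalance. State a rule for missing SpO2, for example a missing-value indicator or oxygen use alone. The Day 0 ordinal score may stay as an additional covariate or as the reference for later change.

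In 2.1, state whether baseline means study entry or the state before infection, and reconcile 2.1 with 7.3 and Appendix 1 on which scale is recorded.

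The cost is wording and a few degrees of freedom in the model. Sections 6.1 and 6.2 already collect both variables, so no new assessment is needed. SpO2 is taken only if possible and the documents do not say how often it will be missing, so the rule must be fixed before unblinding. Pre-dose timing in 6.2 is also only if feasible; a screening value can stand in.

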# 4 Subject Selection, Enrollment, and Withdrawal

#### 4.1 Inclusion Criteria

Subjects must meet *all* of the following inclusion criteria to be eligible for enrollment:

- 1. Men or post-menopausal women age  $\geq$ 65 years.
- 2. Current nursing home resident.
- 3. CoV severity of moderate or less OR SpO2  $\geq$  85% (on room air or  $\leq$  2 L of supplemental oxygen) at time of enrollment.
- 4. SARS-CoV-2 infection confirmed by mRNA-PCR test at Mayo Clinic or other CLIA certified laboratory, within 10 days before randomization.
- 5. Willing and able to provide written informed consent or have a legally authorized representative (LAR) who will provide informed consent.

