# 5.3 Method for Assigning Subjects to Treatment Groups

Subjects will be randomized to either Fisetin or placebo using an internet-based, web browser randomization procedure maintained by the data management team at Wake Forest School of Medicine. Study coordinators access the randomization application through the trial website. Access to this application is password-protected and its communications are encrypted. Once security requirements are satisfied, consent and eligibility of the participant are verified, and randomization will occur. Randomization is controlled centrally based on each potential participant's consent and eligibility status. ONLY eligible participants will have the randomization button displayed. It will be impossible to randomize an ineligible person, or a person for whom screening or consent is incomplete. We will use a permuted block randomization scheme with varying block sizes and without stratification so that group assignment is balanced as the study proceeds, but study personnel will not be able to predict treatment assignment.

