### 5.8 Masking/Blinding of Study

In order to minimize the study bias, this study will use a process for randomized assignment to either active Fisetin or placebo (see Section 5.3). The investigational drug blind will be maintained using the processes of the research or general pharmacy associated with the nursing home for preparation of the investigational product. All subjects and study personnel except for those directly involved with IP preparation will be blinded to IP assignment until the end of the study. All unblinded dosing information must be maintained in a secured area, accessible only by unblinded personnel.

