### 7.3 Determination of Ordinal Scale

The subject's score on the Ordinal Scale for Clinical Improvement (Appendix 1) will be recorded daily (if feasible) through day 14 using the subject's worst assessments of the day. In addition, the score will be recorded on days 30, 90 and 180, if possible.

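### Adjust the primary ordinal model for baseline severity, age and sex in every case, rather than only when they show an imbalance that the plan does not define

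*Combined protocol and SAP*

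**What the plan says.** Section 8.2 specifies an ordinal logistic regression of the 7-point scale, with a two-sided 0.05 Wald test of the treatment coefficient, "after adjusting for key baseline variables such as baseline COVID severity status, age, and sex that show imbalance between the groups". As worded, the three variables are examples, and each enters only if it looks unbalanced. Nothing elsewhere in the document gives a measure of imbalance, a cut-off, a time for the check or someone to make it, and there is no other covariate list for the primary model.

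Section 5.3 does not balance these variables by design: "We will use a permuted block randomization scheme with varying block sizes and without stratification". Section 3.1 allows stratification by antiviral use if such an agent becomes standard of care, but that would not balance severity, age or sex.

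Section 8.1 plans 80% power with 75 per group "to detect a log odd's ratio of 0.81 which translates to an odd's ratio of 2.25 comparing the control to Fisetin group". Its calculation includes no covariates.

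The data needed for adjustment are already scheduled. Sections 6.1 and 6.2 both list "Determination of Ordinal Scale score", at screening and on Day 0, and section 6.1 lists demographics.

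**The concern.** The reason to adjust for a covariate is that it predicts outcome, not that it happens to differ between arms. In a randomised trial any imbalance is due to chance, so a trigger based on it includes a prognostic variable in some trials and drops it from others. When it is dropped, the precision it offered is lost.

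The rule is also incomplete. Two analysts following section 8.2 faithfully could fit different primary models and report different p-values. Checking balance requires the treatment codes, and section 5.8 says that personnel other than those preparing product "will be blinded to IP assignment until the end of the study". The check may therefore fall when outcomes are also known, and only a written rule would then show that the choice did not depend on them.

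The plan is stricter on a secondary endpoint than on the primary one: its regression for senescent cell markers always adjusts for the baseline value.

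**Working it through.** **1. The plan's own power figure.** Inputs from section 8.1: 150 participants in total, controls spread equally over 7 categories, log odds ratio 0.81, two-sided alpha 0.05. By Whitehead's formula, power = Φ(|log OR|·√V − 1.960), with V = (N/12)(1 − Σp³).

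- Σp³ = 7 × (1/7)³ = 1/49 = 0.0204
- V = 12.5 × 0.9796 = 12.245, and √V = 3.499
- Power = Φ(0.81 × 3.499 − 1.960) = Φ(0.874) = 80.9%

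Using the average of the two arms' distributions gives 80.8%. The stated 80% is reproduced, and the sample size is not in question.

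**2. How often a trigger omits a given variable.** A trigger of p<α omits it with probability 1 − α: 95% at 0.05 and 90% at 0.10. For a standardised mean difference (SMD), the standard error is about √(2/75) = 0.163.

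- SMD >0.20: P(|Z| < 0.20/0.163 = 1.225) = 78% omitted
- SMD >0.10: P(|Z| < 0.10/0.163 = 0.612) = 46% omitted

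The simulated figures for severity were 94–95%, 89–90%, 77–79% and 44–46%.

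**3. Power.** This was a proportional-odds simulation with 75 per arm, placebo uniform over 7 categories, and the treatment effect calibrated so that the overall odds ratio is 2.25. There were 10,000 trials per setting (Monte Carlo standard error about 0.4 points). The documents give neither the severity mix nor prognostic strength, so these are assumptions: severity shares 60/40 or 55/35/10; severity odds ratio per level 1, 1.5, 2 or 3; age (per SD) and sex (30% male) both 1.0 or both 1.3. Ranges run over both mixes, the age and sex settings run, and the four triggers. The first row has nothing prognostic.

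| Severity OR per level | Power under a trigger (%) | Power always adjusting (%) | Gain (points) |
|---|---|---|---|
| 1 | 80.1–80.5 | 80.2–80.3 | −0.3 to +0.2 |
| 1.5 | 80.2–81.5 | 80.6–82.2 | +0.1 to +1.5 |
| 2 | 80.3–82.5 | 81.5–83.9 | +0.7 to +3.1 |
| 3 | 80.7–84.6 | 84.1–87.1 | +1.6 to +5.8 |

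The largest gain (87.1 − 81.3 = 5.8) needs the 55/35/10 mix, severity OR 3, age and sex both prognostic, and the p<0.05 trigger. With the 60/40 mix the OR 3 gain is 1.6 to 3.9.

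**4. Dependence on the threshold.** The four triggers disagreed on significance in 2.4% of trials (nothing prognostic) to 7.7% (strongest setting). A smaller simulation, with 3,000 trials in each of four settings, gave 2.4–9.3%. In the strongest setting it gave 80.2–85.0% power under the triggers against 87.6% always adjusting. The upper ends of these ranges are therefore uncertain by one or two points.

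**5. Type I error** (treatment OR 1, age and sex OR 1.3; standard error about 0.2 points). Unadjusted 4.7–5.0%; any one fixed trigger 4.1–5.1%; always adjusted 5.2–5.4%.

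**The case against.** The strongest reply is that this is a matter of efficiency. There is no bias, no inflation from a fixed trigger, and the planned 80% survives. At a severity odds ratio of 1.5 the gain is at most 1.5 points, and the larger gains rest on prognostic strength that the documents do not supply. All of that stands, and the point is graded accordingly.

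The adjusted Wald test also runs slightly above nominal, at 5.2–5.4%. Near 80% power, moving the critical value from 1.960 to 1.943 or 1.927 is worth about 0.017 × 0.280 = 0.5 to 0.033 × 0.280 = 0.9 points. So much of the gain in the OR 1.5 row could come from this rather than from precision. It does not explain most of the OR 3 gains.

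The timing worry is a possibility, not a finding. Staff preparing product are unblinded, and section 9.8 gives the monitoring board unblinded data regularly, so a baseline table by arm could exist before outcomes are complete.

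A reader might infer four stronger points that the documents do not support:

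- *Type I error is inflated.* Choosing the most favourable of four thresholds after seeing results would give 5.6–6.0%, and the best of eight covariate subsets 6.9–8.5%; assuming stronger covariates, the latter reached 11.2%. These are upper bounds for choosing a model by its p-value. Section 8.2 does not propose that, and the subset search ignores imbalance altogether.
- *The trial falls well short of 80% power.* If 2.25 were the effect within severity levels, trigger power in comparable settings (age and sex not prognostic) would be 73.2–79.9%, against 79.7–80.2% always adjusting. Under stronger assumed covariates it would be far lower. But section 8.1 has no covariates and works from the overall control distribution, so 2.25 is best read as the overall effect.
- *Severity is left out of most trials whatever the trigger.* This is untrue for SMD >0.10, which omits it in about 45%.
- *Baseline severity is undefined.* Section 4.1 uses a grade ("CoV severity of moderate or less OR SpO2") and section 3.5 refers to a Table 4 that is absent from the text available here. That table may define the grade, so the absence cannot be held against the plan. The sponsor need only say which recorded measure is meant.

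**Conclusion.** The point holds as a free improvement. Adjustment conditional on an unstated imbalance criterion gives up some precision and leaves the primary p-value dependent on a threshold that the plan does not state. The gain from always adjusting is about 0 to 6 points of power at an overall odds ratio of 2.25, with no detectable loss if none of the variables is prognostic. The significance verdict varies with the threshold in about 2 to 8% of simulated trials.

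The power figures rest on assumed severity mixes and prognostic odds ratios, on proportional odds, and on section 8.1's uniform control distribution. The omission rates in step 2 follow from randomisation and sample size alone. The argument for a fixed covariate list does not depend on any of these assumptions.

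**What to change.** Replace the imbalance clause in section 8.2 with text such as:

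> Baseline COVID severity [sponsor to name the measure recorded at screening or Day 0 before the first dose], age and sex will be included as prespecified covariates in the primary ordinal logistic regression regardless of observed imbalance. If randomisation is stratified by antiviral use (section 3.1), that factor will also be included.

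Keep the unadjusted model as a sensitivity analysis. The 7-point endpoint levels, including their references to baseline, should stay as they are. Make the change before unblinding.

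The cost is two sentences and the naming of one variable. No extra participants or visits are needed, and no extra data if the measure named is the ordinal score already scheduled at screening and Day 0. If the sponsor means a different severity grade, it should confirm that this is recorded before the first dose.
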